4. PARTICIPANT ENTRY

4.1 PRE-REGISTRATION EVALUATIONS

No need for any specific screening tests prior to participant entry into the study.

4.2 INCLUSION CRITERIA

All women presenting to rapid access gynaecology clinic with postmenopausal bleeding or intermenstrual bleeding

4.3 EXCLUSION CRITERIA

Anyone lacking capacity. <18years old. Pregnant. Any contra-indication carry out a biopsy

4.4 WITHDRAWAL CRITERIA

Withdrawal procedure occurs if patients choose to exit the study or if they lose capacity. After withdrawal from the study the anonymised tissue already obtained with consent will remain stored for the duration of the study. In addition, the clinical details up till the point of withdrawal of the patient from the study will remain on file.

5. ADVERSE EVENTS

5.1 DEFINITIONS

Adverse Event (AE): any untoward medical occurrence in a patient or clinical study subject.

Serious Adverse Event (SAE): any untoward and unexpected medical occurrence or effect that:

- **Results in death**
- **Is life-threatening** – refers to an event in which the subject was at risk of death at the time of the event; it does not refer to an event which hypothetically might have caused death if it were more severe

- **Requires hospitalisation, or prolongation of existing inpatients' hospitalisation**
- **Results in persistent or significant disability or incapacity**
- **Is a congenital anomaly or birth defect**

Medical judgement should be exercised in deciding whether an AE is serious in other situations. Important AEs that are not immediately life-threatening or do not result in death or hospitalisation but may jeopardise the subject or may require intervention to prevent one of the other outcomes listed in the definition above, should also be considered serious.

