5.3 REPORTING PROCEDURES

All adverse events should be reported. Depending on the nature of the event the reporting procedures below should be followed. Any questions concerning adverse event reporting should be directed to the Chief Investigator in the first instance.

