5.3.1 Non serious AEs

All such events, whether expected or not, should be recorded.

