5.3.2 Serious AEs

An SAE form should be completed and faxed to the Chief Investigator within 24 hours. However, relapse and death due to endometrial cancer and hospitalisations for elective treatment of a pre-existing condition do not need reporting as SAEs.

All SAEs should be reported to the JCRO at Imperial where in the opinion of the Chief Investigator, the event was:

- 'related', ie resulted from the administration of any of the research procedures; and
- 'unexpected', ie an event that is not listed in the protocol as an expected occurrence

Reports of related and unexpected SAEs should be submitted within 15 days of the Chief Investigator becoming aware of the event, using the NRES SAE form for non-IMP studies. The Chief Investigator must also notify the Sponsor of all SAEs.

Local investigators should report any SAEs as required by their Local Research Ethics Committee, Sponsor and/or Research & Development Office.

Contact details for reporting SAEs
Attention [name]

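### Section 5.1 builds *unexpected* into the SAE definition while 5.3.2 tests it again among SAEs; the two conflict and could leave expected serious biopsy complications outside expedited reporting

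*Combined protocol and SAP*

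**What the plan says.** Section 5.1 defines an adverse event as "any untoward medical occurrence in a patient or clinical study subject", with no condition on expectedness. It defines an SAE as "any untoward and unexpected medical occurrence or effect that" meets one of five criteria: death, threat to life, hospitalisation or its prolongation, disability or incapacity, and congenital anomaly. A catch-all follows. It asks for medical judgement and brings in as serious "Important AEs that are not immediately life-threatening or do not result in death or hospitalisation but may jeopardise the subject" or may need intervention to prevent one of the listed outcomes. It contains no expectedness test.

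Section 5.3 opens with "All adverse events should be reported" and refers the reader to the procedures beneath it. For non-serious events, 5.3.1 says "All such events, whether expected or not, should be recorded". For SAEs, 5.3.2 says "An SAE form should be completed and faxed to the Chief Investigator within 24 hours" and "The Chief Investigator must also notify the Sponsor of all SAEs".

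Section 5.3.2 also exempts relapse and death from endometrial cancer, and elective admissions for a pre-existing condition, from SAE reporting. It sends to the research office, within 15 days, those SAEs that the Chief Investigator considers both related and unexpected. There *unexpected* is explained as "an event that is not listed in the protocol as an expected occurrence".

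**The concern.** Seriousness describes the outcome of an event; expectedness describes what was known beforehand. Section 5.1 merges the two and 5.3.2 keeps them apart. Both the 24-hour form and the sponsor notice depend on an event being an SAE, so the 5.1 wording decides whether they are triggered.

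This matters because of what the study adds to routine care. The Main Study section calls the ultrasound-guided use of the forceps novel, and the Background says that only case reports exist. The Statistics section expects that 80 women will require hysteroscopy and could be offered this biopsy. Other women may give a second pipelle sample or an additional endometrial biopsy at surgery. With so little prior experience, a serious procedural complication is something the Chief Investigator and sponsor need to hear about promptly, whether or not it was foreseeable.

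**Working it through.** There is no figure to reproduce. The check follows one event through Section 5: a complication of a research biopsy that leads to hospitalisation and is regarded as a recognised risk of the procedure.

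| Reading of 5.1 | SAE under the main definition? | 24-hour form and sponsor notice? |
|---|---|---|
| Literal, ordinary sense of *unexpected* | No | Not triggered, unless the catch-all applies |
| 5.3.2 meaning carried back, no list of expected events (present text) | Yes | Both triggered |
| 5.3.2 meaning carried back, a list added that names the event | No | Not triggered, unless the catch-all applies |
| *and unexpected* deleted | Yes | Both triggered, with or without a list |

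**Where the excluded event goes.** Under the first and third readings, 5.3 still asks for all adverse events to be reported, but it names no deadline or recipient and defers to 5.3.1 and 5.3.2. The first covers non-serious events, which are only recorded. The second covers SAEs. A serious event that fails the SAE definition has no clear route.

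**Why the sections conflict.**
1. If every SAE is unexpected by definition, the *unexpected* half of the research-office test in 5.3.2 removes nothing.
2. The 5.3.2 exemptions concern largely foreseeable events. They make most sense if such events would otherwise count as SAEs.

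**The catch-all.** Its two limbs are joined by *or*. Taken literally, an admission that is not immediately life-threatening satisfies the first limb, so an expected admission that may jeopardise the patient could come back in. If *and* was intended, the catch-all reaches only events without death or hospitalisation. Expectedness would then not matter for those lesser events but would exclude the graver ones. On either wording, an expected event that is immediately life-threatening and results in hospitalisation is not covered.

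**The list.** The available text lists no expected biopsy complications. The only trace is a bullet on expected side effects under the example appendices, which is template text.

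**The case against.** The strongest reply is that the documents explain *unexpected* only once, in 5.3.2, within the same Section 5. Apply that meaning throughout and, with no list in the available text, every serious biopsy complication is unexpected, is an SAE, and triggers both safeguards. The surrounding text also points towards reporting: 5.3 covers all adverse events, 5.3.2 names its exemptions and biopsy complications are not among them, and the catch-all has no expectedness test.

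Much of this stands. A reader might infer that expected serious biopsy complications are definitely outside the SAE definition and go unreported. The documents do not support that: it holds only on one reading of 5.1, and even then 5.3 still asks for a report. A reader might also infer that the treating doctor decides what counts as expected. Section 5.1 gives that decision to nobody; its reference to medical judgement concerns seriousness; and 5.3.2 gives the opinion on expectedness to the Chief Investigator, for the research-office report only.

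The reply does not remove the contradiction. Section 5.1 neither defines the word nor refers to 5.3.2, and whether to complete the 24-hour form is settled before the 5.3.2 test is reached. The reassuring reading also depends on the list staying empty, although 5.3.2 presupposes a list and the template invites one.

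**Conclusion.** This is an internal inconsistency between 5.1 and 5.3.2, with a conditional consequence for safety reporting. On a literal reading of 5.1, a serious but expected complication of a research biopsy could miss the 24-hour form and the sponsor notice. On the 5.3.2 meaning, and assuming that no list of expected events exists outside the available text, nothing is excluded now; the gap would open once a list was added.

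Its size cannot be stated. The 80 women are those who could be offered the ultrasound-guided biopsy, not a count of events, and no complication rate is given for any of the research samples. No endpoint, estimate or sample size is affected. The point is still worth correcting, because the protection now depends on a definition borrowed from a later section and on a list that has not been written.

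**What to change.** In 5.1, delete *and unexpected*, so that an SAE is any untoward medical occurrence or effect that meets a listed seriousness criterion. In 5.3.2, keep *related* and *unexpected* as the Chief Investigator's test for the 15-day report to the research office, and nowhere else. The 24-hour form and the sponsor notice then follow from seriousness alone, subject to the exemptions already in 5.3.2, and a later list of expected events would affect only the research-office report.

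The cost is two words and possibly a few more SAE forms. Design, sample size and clinical care are unchanged.

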5.3 REPORTING PROCEDURES

All adverse events should be reported. Depending on the nature of the event the reporting procedures below should be followed. Any questions concerning adverse event reporting should be directed to the Chief Investigator in the first instance.

5.3.1 Non serious AEs

All such events, whether expected or not, should be recorded.

5.3.2 Serious AEs

An SAE form should be completed and faxed to the Chief Investigator within 24 hours. However, relapse and death due to endometrial cancer and hospitalisations for elective treatment of a pre-existing condition do not need reporting as SAEs.

All SAEs should be reported to the JCRO at Imperial where in the opinion of the Chief Investigator, the event was:

- 'related', ie resulted from the administration of any of the research procedures; and
- 'unexpected', ie an event that is not listed in the protocol as an expected occurrence

Reports of related and unexpected SAEs should be submitted within 15 days of the Chief Investigator becoming aware of the event, using the NRES SAE form for non-IMP studies. The Chief Investigator must also notify the Sponsor of all SAEs.

Local investigators should report any SAEs as required by their Local Research Ethics Committee, Sponsor and/or Research & Development Office.

Contact details for reporting SAEs
Attention [name]

6. ASSESSMENT AND FOLLOW-UP

Following surgery patients will continue with routine standard of care and follow up. Patients will be followed up for 5 years to provide 5-year survival data. Images from ultrasound, MRI pelvis and MR spectroscopy will be analysed to see if they can predict the 5-year survival.

End of trial will be defined as when the last patient for recruitment received her operative surgery (and final histology was obtained) and has been followed up for 5 years.

7. STATISTICS AND DATA ANALYSIS

Statistical analysis: Sample size was calculated on the basis of recently published work and anticipated ease of recruitment. It is estimated that approximately 10% of women attending rapid access clinic will have endometrial cancer. In previous studies assessing new endometrial sampling devices a population of 50 women was used. In this population it is expected that 80 women will require a hysteroscopy and could be offered an ultrasound guided biopsy.

Data and all appropriate documentation will be stored for a minimum of 10 years after the completion of the study, including the follow-up period.

8. REGULATORY ISSUES

8.1 ETHICS APPROVAL

The Chief Investigator has obtained approval from the Research Ethics Committee. The study must be submitted for Site Specific Assessment (SSA) at each participating NHS Trust. The Chief Investigator will require a copy of the Trust R&D approval letter before accepting participants into the study. The study will be conducted in accordance with the recommendations for physicians involved in research on human subjects adopted by the 18th World Medical Assembly, Helsinki 1964 and later revisions.

8.2 CONSENT

Consent to enter the study must be sought from each participant only after a full explanation has been given, an information leaflet offered and time allowed for consideration. Signed participant consent should be obtained. The right of the participant to refuse to participate without giving reasons must be respected. After the participant has entered the study the clinician remains free to give alternative treatment to that specified in the protocol at any stage if he/she feels it is in the participant's best interest, but the reasons for doing so should be recorded. In these cases the participants remain within the study for the purposes of follow-up and data analysis. All participants are free to withdraw at any time from the protocol treatment without giving reasons and without prejudicing further treatment.

8.3 CONFIDENTIALITY

The Chief Investigator will preserve the confidentiality of participants taking part in the study and is registered under the Data Protection Act.

8.4 INDEMNITY

Imperial College London holds negligent harm and non-negligent harm insurance policies which apply to this study/ Imperial College Healthcare NHS Trust holds standard NHS Hospital Indemnity and insurance cover with NHS Litigation Authority for NHS Trusts in England, which apply to this study (delete as applicable)

8.5 SPONSOR

Imperial College London/Imperial College Healthcare NHS Trust (delete as applicable) will act as the main Sponsor for this study. Delegated responsibilities will be assigned to the NHS trusts taking part in this study.

8.6 FUNDING

We have applied for funding from the wellbeing of women charity.

8.7 AUDITS

The study may be subject to inspection and audit by Imperial College London under their remit as sponsor and other regulatory bodies to ensure adherence to GCP and the NHS Research Governance Framework for Health and Social Care (2nd edition).

9. STUDY MANAGEMENT

The day-to-day management of the study will be co-ordinated through [name], clinical research fellow.

10. PUBLICATION POLICY

The data obtained from this study will be anonymised and analysed. The anonymised data will be published in peer-reviewed journals and presented in relevant conferences and at patient/public engagement events.

Appendix 1. Summary of investigations & treatment of patient (blue routine, red trial)
